### **6.4.2 Secondary Outcomes**

#### **6.4.2.1 Patient-Reported Outcomes Measurement Information System (PROMIS) Pain Measures**

Raw scores are converted to T-scores are derived using item response theory scoring by HealthMeasures <<https://healthmeasures.net>>. Assessed at Baseline, Post-Intervention, and 1-Month Follow-Up.

##### **6.4.2.1.1 PROMIS Pain Intensity Short Form 3a**

This 3-item instrument assesses how much a person hurts [5]. The first two items assess pain intensity utilizing a 7-day recall period (items include the phrase "the past 7 days") while the last item asks patients to rate their pain intensity "right now." Respondents report their pain on a 5-point scale: 1=Had no pain, 2=Mild, 3=Moderate, 4=Severe, and 5=Very severe. PROMIS Pain Intensity T-scores range from 36.3 (had no pain) to 81.8 (very severe pain).

##### **6.4.2.1.2 PROMIS Pain Interference Short Form 6b**

This 6-item instrument measures the self-reported impact of pain on a person's life and extent to which pain may interfere with engagement with social, cognitive, emotional, physical, and recreational activities over a 7-day recall period [6]. Respondents report levels of pain interference on a 5-point scale: 1=Not at all, 2=A little bit, 3=Slightly, 4=Quite a bit, and 5=Very much. PROMIS Pain Interference T-scores range from 41.0 (no pain interference) to 78.3 (highest pain interference).

##### **6.4.2.1.3 PROMIS Physical Functioning Short Form 10a**

This 10-item instrument measures a patient's abilities and limitations with respect to everyday physical activities like climbing stairs, carrying groceries, and being able to sit on/get up from the toilet [7]. Respondents report limitations on a 5-point scale: 5=Not at all, ..., 3=Slightly, ..., 1=Cannot do, and abilities to perform activities on a 5-point scale: 5=Without any difficulty, ..., 3=With some difficulty, ..., 1=Unable to do. PROMIS Physical Functioning T-scores range from 13.5 (limited physical function) to 61.9 (high physical function).

##### **6.4.2.1.4 PROMIS Fatigue Short Form 6a**

This 6-item instrument assesses a patient's level of fatigue over a 7-day recall period [8].

SAP version 1.0:

Protocol # NCT04869345

February 21, 2023

Page 9 of 19

Respondents are asked to report fatigue on a scale on a five-point scale: 1=Not at all, 2=A little bit, 3=Somewhat, 4=Quite a bit, 5=Very much. PROMIS Fatigue is scored on the T-score metric (higher scores indicate greater pain intensity).

#### **6.4.2.2 Change in Depressive Symptoms as Measured by the Center for Epidemiologic Studies Depression Scale Revised (CESD-R-10)**

The 10-item version of the Center for Epidemiological Studies Depression Scale (CES-D) asks for participants to rate how often over the past week they experienced symptoms associated with depression on a 4-point scale [9]: 0=Rarely or None of the time, 1=Some or Little of the time, 2=Moderately or Much of the time, 3=Most or Almost all the time. CESD-R-10 mean scores range from 0 (rare depressive symptoms) to 4 (depressive symptoms most or almost all the time).

Assessed at Baseline, Post-Intervention, and 1-Month Follow-Up.

#### **6.4.2.3 Change in Stress Appraisal as Measured by the Perceived Stress Scale**

The 10-item version of the Perceived Stress Scale (PSS) assesses the perception of stress over the previous month [10]. Respondents report how often they have experienced perceived stress on a five-point scale: 0=Never, 1=Almost never, 2=Sometimes, 3=Fairly often, 4=Very often. PSS mean scores range from 0 (experienced no or minimal stress) to 4 (experienced very frequent stress).

Assessed at Baseline, Post-Intervention, and 1-Month Follow-Up.

#### **6.4.2.4 Change in Positive Affect as Measured by the Modified Differential Emotions Scale (mDES)**

The modified Differential Emotions Scale (mDES) is a 20-item instrument that measures the extent to which a patient has experienced positive and negative emotions over a chosen time frame; in the version used in this study, we ask for emotions over the past 7 days [11]. Respondents are asked to report the greatest amount of a given emotion on a five-point scale: 0=Not at all, 1=A little bit, 2=Moderately, 3=Quite a bit, 4=Extremely. mDES mean scores range from 0 (not at all experienced positive emotion) to 4 (extremely positive emotion). Assessed at Baseline, Post-Intervention, and 1-Month Follow-Up.

#### **6.4.2.5 Change in Positive Affect as Measured by the Positive and Negative Affect Scale (PANAS-GEN)**

The 20-item self-report Positive and Negative Affect Scale (PANAS-GEN) asks participants to describe to what extent they feel different feelings and emotions on average [12]. Respondents answer on a five-point scale: 0=Very slightly or not at all, 1=A little, 2=Moderately, 3=Quite a bit, 4=Extremely. PANAS-GEN mean scores range from 0 (very slightly or not at all positive affect) to 4 (extremely positive affect). Assessed at Baseline, Post-Intervention, and 1-Month Follow-Up.

#### **6.4.2.6 Daily Survey Assessments**

Assessed over 7-day periods at Baseline, Post-Intervention, and 1-Month Follow-Up.

##### **6.4.2.6.1 Change in Affective Reactivity to Stress as Measured by the Daily Modified Differential Emotions Scale (mDES)**

A 20-item instrument that measures the extent to which a patient has experienced positive and negative emotions over a chosen time frame; in the version used in this survey, we ask for emotions over the past 24 hours [11]. Respondents are asked to report the greatest amount of a given emotion on a five-point scale: 0=Not at all, 1=A little bit, 2=Moderately, 3=Quite a bit, 4=Extremely. mDES mean scores range from 0 (not at all experienced positive emotion) to 4 (extremely positive emotion).

**6.4.2.6.2      *Change in Affective Reactivity to Stress as Measured by the Daily Inventory of Stressful Events (DISE)***

A 7-item self-report instrument in which participants report whether stressful events have occurred within the past 24 hours, indicating 1=yes or 0=no accordingly [13].

**7      Sample Size**

Given that the primary purpose of this study is to assess the feasibility of methods and procedures to be used in a larger, fully powered trial of LARKSPUR, sample size was chosen based on feasibility indicators (recruitment, retention, adherence) rather than on formal power calculations, as appropriate for the pilot nature of the study [see 1]. For quantitative pilot studies, sample sizes of 30 per treatment arm have been proposed to establish feasibility [2]. To allow for attrition between end-of-trial and follow-up, we aimed to recruit 45 per group (intervention and control). Findings from subgroup analyses should therefore be interpreted with caution and call for further confirmatory randomized trials [3].

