This document is confidential and is to be distributed for review only to investigators, potential investigators, consultants, study staff, and applicable independent ethics committees or institutional review boards. The contents of this document shall not be disclosed to others without written authorization from WCM.

Weill Cornell Medicine

Institution Name

M. [name], PhD

June 29, 2021

Principal Investigator's Name

Principal Investigator's Signature

Date

List of Abbreviations

AE	Adverse Event
CFR	Code of Federal Regulations
COA	Center on Aging
CRF	Case Report Form
CTSC	Clinical Translational Science Center
FDA	Food and Drug Administration
FMS	FibroMyalgia Syndrome
GCP	Good Clinical Practice
HIPAA	Health Insurance Portability and Accountability Act of 1996
ICF	Informed Consent Form
IRB	Institutional Review Board
LARKSPUR	Lessons in Affect Regulation to Keep Stress and Pain UndeR control
NYP	NewYork-Presbyterian
PA	Positive Affect
PHI	Protected Health Information
PI	Principal Investigator
REDCap	Research Electronic Data Capture
WCM	Weill Cornell Medicine

1. Protocol Summary

Full Title:	Positive Affect as a Source of Resilience for Adults in Chronic Pain
Short Title:	LARKSPUR Study
Principal Investigator:	M. [name], PhD (WCM) [name] (Cornell)
Study Description:	Our goal for this study is to evaluate the feasibility, acceptability, and effect size of a previously developed online positive affect (PA) skills intervention—LARKSPUR (Lessons in Affect Regulation to Keep Stress and Pain UndeR control)—in a sample of older adult patients with fibromyalgia syndrome (FMS).
Sample Size:	N= 150
Enrollment:	This study will enroll 150 subjects and screen up to 1,200 subjects
Study Population:	Older adults 50 years of age or older with a physician confirmed diagnosis of FMS, or a self-report physician diagnosis corroborated by a screening measure, that will be stratified by Hispanic, non-Hispanic Black, or non-Hispanic other (e.g., White, Asian).
Enrollment Period:	2 years
Study Design:	This is a longitudinal, randomized behavioral intervention feasibility study with internet trainings, daily reporting, and surveys using REDCap and BrightOutcome for data collection.
Description of Sites/ Facilities Enrolling	
Participants:	We will be enrolling participants only through WCM/NYP and will be recruiting participants through EPIC, physician referral, flyers, letters, social media, and direct recruitment.
Study Duration:	September 30, 2024

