- Week 4: Positive Reappraisal and Gratitude
- Week 5: Acts of Kindness
- Week 6: Wrap-Up

The following table is the LARKSPUR intervention content.

Table 1. Intervention Content

Week 1	Noticing and Savoring Positive Events	Recognizing cognitive biases that can lead to discounting or failing to remember positive events. Skills for scheduling pleasant events according to level of pain
	Exercises	Daily positive events journal
Week 2	Strengths and Activation	Support for acknowledging strengths even in the presence of pain-related limitations. Emphasis on setting small, attainable goals and working up to challenging goals gradually. How to select goals that will provide pleasure or mastery experiences.
	Exercises	Daily strengths journal (record ways a personal strength or talent was used) Activity journal
Week 3	Mindfulness	Using present-focused awareness to combat rumination about chronicity of pain and pain-related limitations Using acceptance to tolerate unpleasant situations with less negative emotion
	Exercises	Select an everyday activity to do mindfully Mindful breathing recorded meditation (10 minutes)
Week 4	Positive Reappraisal and Gratitude	Role of negative cognitions in causing or maintaining stress and contributing to pain
	Exercises	Daily reappraisal journal Daily gratitude journal
Week 5	Acts of Kindness	Include benefits of compassion toward self and others (e.g., decreased stress and pain; improved relationships) Small prosocial acts that can be performed even if one is relatively socially isolated or has limited mobility
	Exercises	Do something nice for someone else each day and record it in a daily kindness journal
Week 6	Wrap-Up	Review the LARKSPUR course, reflect on skills learned, and make a plan for continued practice.

Randomization. Once participants complete consent and baseline questionnaire, participants will be randomized 1:1 to LARKSPUR (n = 75) or an emotion reporting only attention control condition (n = 75) stratified by race/ethnicity. The random number sequence will be generated and uploaded into REDCap by a non-data collecting co-investigator under the guidance of the study statistician and REDCap/CTSC personnel. All participants will know their intervention/attention control status.

LARKSPUR intervention (n = 75). The LARKSPUR intervention will be based on our current online positive affect intervention which consists of skills for increasing the frequency of positive emotions, beginning

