with basic skills for recognizing and savoring positive events and progressing to more complex skills such as goal-setting and acts of kindness.

A week will consist of 1-2 days of didactic material and 5-6 days of real-life skills practice and reporting. Participants cannot skip ahead and can only progress to the next lesson if they have completed the current one, but they can return to old lessons or exercises if they choose. As part of the daily home practice, intervention participants will be asked to complete the daily emotion check-in that comprises the attention control condition (which takes about 5 minutes to complete). Based on past studies, we estimate the time to read through a skill to be about 15 minutes per skill. We also encourage daily interaction with the website (home practice, reporting emotions) and estimate the time involved to be an additional about 10 minutes. Both the LARKSPUR intervention and emotion-reporting attention control conditions, including all home practice and assessments, will be done over the internet from the participant's home, or any other location of their choice. The intervention content, emotion check-in, and are all mobile-enabled so can be completed on desktop, laptop, tablet, or smartphone with web browser access.

Attention Control Condition (n = 75). We sought an attention control condition that provided something to engage participants, but was not expensive or burdensome. In past research we have established that emotion reporting is acceptable as an attention control condition (retention rates of ~80%, similar to or higher than for the intervention), and that participants perceive it as being beneficial, providing some of the features of a placebo control. In this daily emotion-reporting attention control condition, participants will be asked to report how they are feeling daily for 6-8 weeks which will be emailed to control participants.

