4.4 Strategies for Recruitment and Retention

We will recruit fibromyalgia patients from offices at Weill Cornell Medicine/NewYork-Presbyterian (e.g., the Center on Aging (COA), the Cornell Internal Medicine Associates (CIMA), and the Iris Cantor Health Center). Co-PI [name], PI of the Cornell Roybal Center, has established a successful track record recruiting chronic pain patients for Roybal-supported research studies at Weill Cornell Medicine/NewYork-Presbyterian.

A total of 150 fibromyalgia patients will be recruited across Aims 1-2 once they have been identified by research and referring physicians confirmed to meet eligibility criteria. Based on prior recruitment at WCM/NYP we anticipate recruiting double the number of females than males, and will target enrollment to an equal number of non-Hispanic Black, Hispanic, or non-Hispanic other (e.g., White, Asian) equally between males and females. Participants will open-endedly self-report their race and ethnicity; the research team will ensure that the randomization process is stratified by Hispanic, non-Hispanic Black, and non-Hispanic other (e.g., White, Asian).

Normal patient participants will be recruited via physician-referred agree to contact sheets (paper or REDCap survey), flyers, and/or in-person recruitment. Physicians will utilize an Agree to Contact sheet that potential participants fill out with their contact information (phone, email, and/or mailing address) and sign agreeing to be contacted directly for the study by any of these methods.

Flyers will be distributed throughout WCM/NYP locations (including the Center on Aging), and distributed at senior centers, community centers, and community events. Additionally, co-investigators may approach potential participants in WCM/NYP offices (e.g. the Center on Aging), and ask if they would be interested in the study, when it is safe to do so under COVID-19 considerations. Trained co-investigators may either screen the participants at recruitment sites and/or ask for their contact information via the Agree to Contact sheet to be followed up at a time convenient for the potential participant.

Research staff will ask physicians at WCM/NYP, to review their patient lists and identify potential participants based on eligibility criteria both directly (e.g. email) and at department meetings. Research staff may also request EPIC provider reports based on eligibility requirements to reach out

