#### **4.2 Scope of the analyses**

**Aim 1.** Feasibility and acceptability will be examined by conducting frequency and descriptive statistics (i.e., mean, median, standard deviation, range) for enrollment rates, number of sessions completed, number of weeks required to complete the intervention, and Likert-scale items assessing satisfaction with the intervention and perceived helpfulness.

**Aim 2.** Aim 2 will be addressed using a pre-post design. To determine the degree to which the LARKSPUR intervention is likely to improve patient outcomes, a post-versus-pre-difference will be sought to estimate the change in patients' outcomes (e.g., pain self-management). This is a small feasibility trial to explore the acceptability and feasibility of the intervention among racially and ethnically diverse older adults with fibromyalgia. The trial is not powered to estimate statistically reliable differences in outcomes.

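### The protocol plans 150 participants (75 per arm), but the SAP gives a recruitment aim of 45 per group (90), and nothing in the available text reconciles the two

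*SAP*

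**What the plan says.** The protocol, dated June 29, 2021, gives the same target in three sections of text:

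- Section 1 (Protocol Summary): "This study will enroll 150 subjects and screen up to 1,200 subjects".
- Section 3 (Randomization): 1:1 allocation to "LARKSPUR (n = 75) or an emotion reporting only attention control condition (n = 75) stratified by race/ethnicity". The two arm descriptions in section 3 repeat 75 each.
- Section 4.4 (Recruitment and Retention): "A total of 150 fibromyalgia patients will be recruited across Aims 1-2".

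SAP section 7 starts from a published suggestion of 30 per arm for pilot studies and continues: "To allow for attrition between end-of-trial and follow-up, we aimed to recruit 45 per group (intervention and control". It names no attrition rate. No other section of the SAP gives a target sample size, and none mentions 150, 75 or a change of target.

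Both documents disclaim power. SAP section 4.2 puts it this way: "The trial is not powered to estimate statistically reliable differences in outcomes".

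**The concern.** Recruitment is part of the primary objective, and SAP section 7 says the sample size was chosen on feasibility grounds, recruitment among them. The planned number is therefore a figure the trial will be judged by. With two targets in force, an enrolment of 90 could be reported as the target met (against the SAP) or as 60% of the target (against the protocol). The recruitment endpoint in SAP section 6.4.1.1 does not settle this, because its percentage is taken over people recruited and not over the planned number. The precision to be expected from the pilot estimates, which are meant to inform a larger trial, also differs between the two figures.

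**Working it through.** **1. Totals.** Protocol: 2 × 75 = 150, which agrees with the 150 in sections 1 and 4.4. SAP: 2 × 45 = 90. Difference: 150 − 90 = 60; 60/150 = 40%; 90/150 = 60%.

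**2. Could the two numbers describe different things?**

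- *Screened versus enrolled.* No. The screening ceiling is 1,200, and 150 is the number enrolled.
- *150 over both aims, with a smaller randomised part.* No. Protocol section 3 randomises 75 + 75.
- *45 as a completer target.* No. SAP section 7 calls it a recruitment aim and reaches it by adding an allowance for attrition to 30.

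**3. Could attrition link them?** The only retention rate in the documents is in Protocol section 3, for the control condition in past research: "retention rates of ~80%, similar to or higher than for the intervention".

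- From 75 recruited: 75 × 0.80 = 60 retained. Falling to 45 needs a loss of 1 − 45/75 = 40%.
- From 30 completers to 45 recruited: implied loss 1 − 30/45 = 33.3%. At 20% loss the result would be 30/0.80 = 37.5, or 38. The SAP states no rate, so its step from 30 to 45 cannot be reproduced.
- From 30 completers to 75 recruited: implied loss 1 − 30/75 = 60%.

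No rate in the documents leads from one target to the other.

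**4. What the difference means for precision.** At any common retention, interval widths for a difference in means scale as 1/√n, so the ratio is √(75/45) = 1.29.

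Illustration, unadjusted, in SD units: half-width = 1.96 × √(2/m), where m is the number of completers per arm. Retention is assumed equal in both arms; 80% is the protocol's past control-arm figure, and the 70% to 90% range is an assumption.

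| Retention | m from 75 | Half-width | m from 45 | Half-width |
|---|---|---|---|---|
| 70% | 52.5 | ±0.38 | 31.5 | ±0.49 |
| 80% | 60 | ±0.36 | 36 | ±0.46 |
| 90% | 67.5 | ±0.34 | 40.5 | ±0.44 |

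The baseline adjustment planned in SAP section 10 would narrow both columns.

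**The case against.** The strongest reply is that little depends on this number. The planned tests and the enrolment percentage do not take the target as an input, neither document sets a precision goal, and the trial is declared not powered for outcomes. All of that stands and limits the weight of the point. A 40% gap in the planned size of a feasibility trial is still more than cosmetic.

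A second reply is that the SAP is about 20 months later than the protocol, so the target may have been lowered in between. That is possible. Some front pages of the documents are not in the public text, and a later protocol version could exist. But Protocol section 7.2.1 requires agreed amendments to be recorded and submitted for ethics approval, and the available text shows no such change.

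Three stronger readings are tempting, and the documents support none of them:

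- *The trial fell short, and the SAP target was fitted to what had been achieved.* The SAP's past tense invites this inference, but neither document gives an achieved enrolment.
- *A reader has no way to tell whether recruitment went to plan.* This is too strong. The protocol's 150 is the only protocol target available and can serve as the benchmark. What is unclear is why the SAP differs and which figure the sponsor holds to.
- *Enrolment is over, or should not continue.* The documents do not say that enrolment has closed. The protocol gives a two-year enrolment period and a study end of September 30, 2024, after the SAP date.

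**Conclusion.** The point holds as an inconsistency between the documents: 150 (75 per arm) in the protocol against 90 (45 per group) in the SAP, 60 participants or 40% apart. It is not an arithmetic slip within either document, and it is not a power error, since no power calculation exists.

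The totals follow from the text alone. The precision figures (about 1.29 times wider intervals; for example ±0.46 against ±0.36 SD) are illustrations that assume equal retention in both arms and no baseline adjustment. The finding that nothing reconciles the figures covers only the text available for review. It should be fixed, because recruitment is a primary feasibility question, but no planned test changes with it.

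**What to change.** State one target in both documents.

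- **If 150 stands:** change the SAP section 7 figure from 45 to 75 per group and rewrite the rationale. Replacing the number alone is not enough, because going from 30 to 75 by attrition would imply a 60% loss.
- **If the target was reduced to 90:** amend Protocol sections 1, 3 and 4.4, record when and why the change was made, state the attrition rate behind 45, and report recruitment against the protocol's 150 as well as the revised figure.

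The cost is a wording change in the SAP or a protocol amendment. The downside is that recruitment may have to be reported as short of 150. The fix asks for no enrolment beyond the protocol's own 150 and takes no position on whether enrolment should continue.
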